1 **Hyperopia Treatment Study (HTS1)**
 2 **Immediate versus Delayed Treatment In Children with Moderate**
 3 **Hyperopia**

4
 5 **Statistical Analysis Plan**
 6 **Version 3.0**

7
 8
 9
 10 Statistical Analysis Plan Version: 3.0, 25Jul18
 11 Protocol Version: 3.0, 28Jan15

12
 13
 14 **VERSION HISTORY**

The following table outlines changes for the analysis plan:

VERSION NUMBER	AUTHOR	APPROVER	EFFECTIVE DATE	REVISION DESCRIPTION*
1.0	[name]	[name]	12-19-17	Initial draft written after study was completed but before manuscript was written.
2.0*	[name]	[name]	05-14-18	Lead authors decided to redefine “best” stereoacuity and visual acuity at the 3-year outcome visit to be consistent with what was done for the IXT study. When preparing to unmask the study investigators to the results, the leads realized that it was not our intent to compare deterioration rates between the two groups. In the planning phase, the planning committee felt the deterioration rates in each group would aid in interpreting the results. The committee felt a formal statistical comparison was not needed because the rate of deterioration was expected to be higher in the observation group than in the glasses group.
3.0*	[name]	[name]	07-27-18	Lead authors decided to redefine best stereoacuity and best visual acuity at the 3-year outcome visit as the best of measurements reported with and without trial frames, during the initial assessment and retest, if required. During their final review of the manuscript, the leads realized that results reported for primary and secondary analyses were discordant. The leads determined that the definitions of best stereoacuity and best visual acuity needed updating to reflect the study design and to be in concordance with results reported in the primary analysis.

* indicate in the description if the changes were made after review of outcome data

15 **1.0 Primary Objective**

16 The primary study objective is to compare visual outcomes and development of strabismus after a
17 36-month follow-up period in two age cohorts (children age 12 to <36 months and children age
18 36 to <72 months) with moderate hyperopia (spherical equivalent +3.00D to +6.00D in either
19 eye) who are prescribed glasses either immediately or only after pre-specified deterioration
20 criteria are met.

21
22 **2.0 Primary Analysis**

23 The primary analysis will be a treatment group comparison of the proportion meeting failure
24 criteria (below) at 36 months post-randomization. The primary analysis will be performed
25 separately for each of the two primary cohorts.

26
27 The null hypothesis of no difference between the treatment groups will be rejected if the
28 proportion meeting failure criteria in immediate glasses is significantly lower or higher than the
29 proportion in observation, based on the Barnard's exact test with 2-sided type I error of
30 $\alpha=0.05$.

31
32 Although Fisher's exact test was initially proposed, this was changed to Barnard's exact test to
33 allow for the calculation of a confidence interval on the difference between proportions, which is
34 consistent with the p-value from the test.

35
36
37 **2.1 Primary outcome**

38 At the 36-month outcome visit, each subject's condition will be classified as either failure or not
39 failure as follows:

40
41 Failure = ANY of the following criteria are met at the masked 36-month visit both with and
42 without correction in trial frames (without prism or bifocal):

- 43
- 44 1. Any measurable heterotropia in primary gaze in the distance (3 meters) or at near (1/3
45 meter) not correctable with distance refractive correction alone
 - 46 2. Strabismus surgery prior to the 36-month outcome exam
 - 47 3. Visual acuity below age norms in either eye
48 a. To be below age-normal, visual acuity in the eye must fall below age-normal
49 values on both test and retest, both with and without correction.
50 b. Visual acuity will be obtained for each eye.
 - 51 4. ≥ 2 logMAR lines of IOD if visual acuity is 20/25 or worse in the better eye (applies to
52 IOD either with or without correction but not one eye with and one eye without)
 - 53 5. ≥ 3 logMAR lines of IOD if visual acuity is 20/20 or better in the better eye (applies to
54 IOD either with or without correction, but not one eye with and one eye without)
 - 55 6. Stereoacuity at near by Randot Preschool test below age normal values

56
57 Not Failure = NONE of the criteria for failure are met

58
59 If a subject meets any failure criteria (with the exception of strabismus surgery prior to the 36-
60 month outcome exam), the visual condition that is considered to be failed must be retested by the
61 masked examiner (*section 3.6.1*) using the same procedures outlined in *section 3.6.1* of the
62 protocol. The subject must be given a 10-minute break prior to retesting each failed criterion.
63 Failure criterion must be confirmed by a retest both with and without correction to be considered
64 a failure.

66 If failure is confirmed and the subject requires a change in glasses (*section 4.3* of the protocol),
67 the 36-month outcome exam is repeated on a different day 4 weeks \pm 1 week later (subsequently
68 referred to as the 37-month visit) by the masked examiner with the child wearing their new
69 glasses. Testing without correction does NOT need to be repeated. Failure will be assessed at this
70 post-36 month exam, and the subject will be classified as a failure if he/she meets any of the
71 failure criteria above. If the subject meets any failure criteria (with the exception of strabismus
72 surgery), the visual condition that is considered to be failed must be retested by the masked
73 examiner using the same procedures outlined above. Failure must be confirmed without
74 correction at the 36-month exam and with correction at this repeat outcome exam 4 weeks later to
75 be considered a failure.

77 **2.2 Principles to be Followed in Primary Analysis**

78 The following principles apply to the primary treatment comparison:

- 79 1. The primary treatment comparisons will be performed using a modified “intent-to-treat”
80 analysis principle. The data of all randomized subjects completing the 36-month exam
81 will be included in the analysis regardless of whether the assigned treatment was actually
82 received. Data from subjects who receive alternate treatment (i.e. glasses for subjects
83 assigned to observation who did not meet deterioration criteria and vice versa) will be
84 analyzed according to randomization group. There will be no imputation of data for
85 subjects who are lost to follow-up or withdrawn from study prior to the primary outcome,
86 defined as the failure status at the 36-month visit if the 37-month visit is not required and
87 failure status at the 37-month visit if required.
- 88 2. Subjects who meet failure criteria at the 36-month assessment and have significant
89 changes in their cycloplegic refraction are prescribed glasses and required to return
90 within 4 weeks to be retested in their updated correction. If this happens, the results of the
91 36-month examination without correction and the 37-month examination with correction
92 will be used to determine failure status in the primary analysis.
- 93 3. Subjects will be included in analysis as long as the 36-month visit was completed. Seeing
94 as failure must be confirmed, subjects who complete the 36-month visit will not be
95 considered to have met failure criteria for a condition if a required test or retest was not
96 performed.
- 97 4. Data will be considered missing if not completed within the analysis window. The 36-
98 month assessment must be completed no earlier than 33 months (1005 days) and no later
99 than 42 months (1282 days). Subjects will be excluded from analysis if the 36-month
100 visit is not completed within the analysis window.
- 101 5. The 37-month visit is an extension of the 36-month visit. No analysis window is defined
102 for the 37-month visit. If required and collected, data at the 37-month visit will be used in
103 analysis. Subjects will be included in analysis if the 36-month visit was completed within
104 the analysis window. See Table 1 and Figure 1 below for clarification.
- 105 6. Imbalances between groups in important covariates measured at baseline are not expected
106 to be of sufficient magnitude to produce confounding. However, as a complement to the
107 primary analysis, the presence of confounding will be evaluated by including in the
108 model factors that appear to be imbalanced between treatment groups and are associated
109 with visual acuity, stereoacuity, or strabismus.

110
111 Barnard’s exact test does not allow for the adjustment of covariates. Binomial regression was
112 used to compare treatment groups when the model was adjusted for possible confounders.

Table 1: Analysis of Data based on Visit Completion

36-Month Visit			37-Month Visit Required	37-Month Visit Completed	Primary and Secondary Analyses ^a	Additional Approaches to Primary Analysis (Imputation) ^b
In Window	Out of Window	Not Completed				
-	-	X	-	-	Excluded	Impute
X			No	-	Data included	Data included
X			Yes	Yes	Data included	Data included
X			Yes	No	Data included	Impute
	X		No	-	Excluded	Impute
	X		Yes	Yes	Excluded	Impute
	X		Yes	No	Excluded	Impute

X indicates when visit was completed

-Visits are considered completed if data was collected at the visit. Completion status is not dependent on the amount of data collected at the visit.

[figure not shown]
^aSubjects will be included in the primary and secondary analyses as long as the 36-month visit was completed. Seeing as failure must be confirmed, subjects who complete the 36-month visit will not be considered to have met failure criteria for a condition if a required test or retest was not performed.

^bData **will not** be imputed for subjects who have met failure criteria, even if all required testing (initial and retest, with and without correction) has not been completed. If failure criteria were met for any condition, the subjects is considered a failure at 36 months.

Table 2: Defining Color Code

Color	Meaning
	Data included
	Data excluded
	Data imputed

Figure 1: Assessment of Failure in Primary Analysis

*Note: Visits are considered to be completed if any data was collected for the subject at the visit. It does not mean that all required testing was performed at the visit.

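### *Best* visual acuity and stereoacuity were redefined after discordant results were seen, and the sections that use them carry no post hoc label and no analysis under the earlier definition

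*SAP*

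**What the plan says.** The SAP's version history has three entries.

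- **Version 1.0 (12-19-17)** is described as "Initial draft written after study was completed but before manuscript was written".
- **Version 2.0 (05-14-18)** changed *best* stereoacuity and acuity to match another study. The same entry drops the formal comparison of deterioration rates and places that decision in time with "When preparing to unmask the study investigators to the results". It does not say whether its change of *best* came before or after outcome results were seen.
- **Version 3.0 (07-27-18)** changed *best* again. At final manuscript review "the leads realized that results reported for primary and secondary analyses were discordant", and the definitions "needed updating to reflect the study design and to be in concordance with results reported in the primary analysis".

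Versions 2.0 and 3.0 carry an asterisk. Its footnote asks authors to "indicate in the description if the changes were made after review of outcome data".

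Sections 3.2 and 3.5 define *best* as the smallest of the readings with and without trial frames, at first test and any retest. Sections 3.3 and 3.6 adopt that value by cross-reference. Section 4.1 uses best acuity to compute the interocular difference, and section 4.4 uses best acuity and stereoacuity as outcomes. Sections 3.0 and 4.0 set the significance level at 0.01. The repeat analyses in section 2.3 concern the primary failure endpoint only.

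**The concern.** One of the two stated reasons for the version 3.0 definition is agreement with a result already known. An endpoint definition chosen with results in hand can move the estimates that depend on it. The usual protection is to say so where the endpoint is defined and to show the results under the definition it replaced. The analysis sections do neither.

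A second issue follows from the form of the new definition. If the age-normal endpoints in 3.3 and 3.6 are nearly the reverse of two primary failure criteria, a reader who sees them agree with the primary result may take that as separate support when most of it follows from the definition.

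**Working it through.** No published figure is at issue, so the check is mainly textual.

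**1. Timing.** From 12-19-17 to 05-14-18 is 146 days, and from 05-14-18 to 07-27-18 is 74 days. So *best* changed twice within 146 + 74 = 220 days of version 1.0, which itself came after study completion.

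**2. Label and comparison.** Sections 3.2, 3.3, 3.5, 3.6, 4.1 and 4.4 were read for any note that the definition followed review of results, and for any analysis under an earlier definition. There is none. The nearest item, the initial-assessment repeat in section 2.3 item 2, applies to failure status and not to best acuity or stereoacuity.

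**3. Relation to the primary outcome.** Let x1, ..., xk be a child's readings for one eye in logMAR, or for stereoacuity in arcseconds, where larger is worse. Let T be the age-normal limit. Then min(x1, ..., xk) > T exactly when every xj > T. So *best* is below norm only if all readings are. Compare the failure rules in section 2.1:

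- Criterion 3a requires an eye to be below age-normal "values on both test and retest, both with and without correction".
- The confirmation rule asks the same of stereoacuity under criterion 6.
- When a 37-month visit is needed, failure must be confirmed without "correction at the 36-month exam and with correction at this repeat outcome exam 4 weeks later to" count. Sections 3.2 and 3.5 likewise combine the 36-month readings without trial frames with the 37-month readings.

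On the 36-month path with all required tests done:

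- If either first reading passes, *best* is within norm and the criterion is not met.
- If both fail and either retest passes, the result is the same.
- If all four fail, *best* is below norm and the criterion is met.

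Section 3.3 requires both eyes to be normal and criterion 3 requires either eye to fail, so these are complements as well. The match therefore supports the stated design reason. It also shows that 3.3 and 3.6 carry little information separate from criteria 3 and 6.

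**4. Possible departures, both conditional.**

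- *A required retest or 37-month visit is missing.* Table 1 note a says such a child "will not be considered to have met failure criteria for a condition if a required test or retest was not performed", while the minimum of the available readings could still be below norm. But the note sits under a column covering primary and secondary analyses, and section 3.0 applies section 2.2 to the secondary analyses. On that reading the departure may vanish.
- *A condition passes with correction but fails without it at 36 months, and another criterion triggers the 37-month visit, where the condition fails test and retest with correction.* This departs only if a single initial failure does not trigger a retest. The SAP refers to protocol section 3.6.1 for the procedures and does not settle the trigger itself.

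**5. Size of the fix.** Section 3.2 has 2 comparisons (better-seeing and worse-seeing eye), and 3.3, 3.5 and 3.6 have 1 each: 2 + 1 + 1 + 1 = 5. Over two cohorts, 5 x 2 = 10 per earlier definition, or 20 if versions 1.0 and 2.0 are both reported.

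**The case against.** The strongest reply is that nothing is concealed. The version table stars version 3.0, dates the change to final manuscript review, and names the discordance and both reasons. That stands: a reader might infer from the analysis sections alone that the change was hidden, and the version history contradicts this. What remains is that disclosure at the front of the SAP does not tell the reader how far the estimates moved.

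The second reply is that the definition is sound. The minimum rule follows the confirmed-failure rule, so the design reason can be checked and holds up. This also stands, and it is why the definition should be kept.

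Third, the earlier definitions are an imperfect yardstick, because all three versions postdate study completion. That limits how the added results can be read. It does not remove their use in showing how sensitive the estimates are to the change. Results under an earlier definition were probably already produced, since their discordance with the primary prompted the revision.

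**Conclusion.** The concern holds for secondary and exploratory reporting. The definition of *best* was adopted after results were seen, partly to agree with the primary results, and the sections that use it neither say so nor show results under the prior definition. With complete 36-month data, agreement of 3.3 and 3.6 with the primary result is mostly built in and is not independent confirmation.

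The effect on the estimates cannot be sized, because the SAP shows neither data nor the version 1.0 and 2.0 definitions. The primary outcome does not use *best* and is unaffected.

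Two stronger readings are tempting and are not supported:

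- **That the definition was changed to alter a treatment effect.** The log does not say whether the discordance lay in treatment effects or in how children were classified, and it also gives a design reason that fits section 2.1.
- **That 3.3 and 3.6 are known to conflict with criteria 3 and 6 in particular cases.** Both candidate situations depend on how Table 1 note a and the retest trigger are read.

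**What to change.** Keep the version 3.0 definition, and:

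1. State in 3.2, 3.3, 3.5 and 3.6 that it was adopted after review of results. Carry the same label to 4.1 and 4.4.
2. Report 3.2, 3.3, 3.5 and 3.6 under the version 2.0 definition beside version 3.0, stating that definition in full. Add version 1.0 if it differs.
3. Say in the report that 3.3 and 3.6 overlap with failure criteria 3 and 6, so their agreement with the primary result is not to be read as independent confirmation.

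The cost is some SAP wording and 10 added comparisons (20 with version 1.0), with no new data. The downside is a slightly longer report and a less tidy secondary result, set against earlier definitions that are not a clean prespecified benchmark.

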2.3 Additional Approaches to Primary Analyses

The primary treatment comparisons will be repeated in the following ways:

1. Include data only from subjects who complete the 36-month visit within the protocol window (34 to 38 months after randomization).
2. The primary analysis will be repeated, using only the initial assessments to identify failure at 3 years. If a change in refractive correction was necessary after formal failure criteria were met and confirmed by a retest, measurements reported for initial assessments performed with trial frames at the 37-month visit will replace measurements reported with trial frames at the 36-month visit if the assessment was failed.
3. The primary analysis will be repeated, imputing data for subjects with incomplete or no data at the primary outcome visit. Data will be imputed for subjects classified as “not failure” at 3 years who meet any of the following criteria: 1) the 36-month visit was not completed or was completed out of window, 2) a required 37-month visit was not completed, 3) an initial assessment or required retest was not performed and the available data indicates that the subject is a failure, or 4) no data was reported for an assessment, or an eye in the case of visual acuity. The imputation procedure is described in section 2.5.
4. The primary analysis will be repeated, adjusting for age at 36-month visit. Barnard’s Exact test does not allow for adjustment. Instead, binomial regression will be used to obtain the adjusted difference in failure rate between the treatment groups. If the model does not converge, Poisson regression using robust variance estimation will be used instead. If the Poisson model does not converge, logistic regression will be used to test the difference in treatment groups, controlling for age.
5. The distribution of the following baseline factors will be reviewed by treatment group: age, visual acuity, and stereoacuity. If factors appear to be confounders, defined as imbalance between treatment groups, binomial regression will be used to evaluate the treatment group difference in failure rates, controlling for all confounding factors. The characteristics will be categorized as follows:
 - a. Age: 1 to <2, 2 to <3, 3 to <4, 4 to <5, 5 to <6 years
 - b. Visual acuity: 20/20 or better, 20/25, 20/32, 20/40, 20/50
 - c. Stereoacuity: 40, 60, 100, 200, 400

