5.0 General Principles for Analysis

5.1 Classifying Visits

The analysis visit window for the randomized clinical trial will be as follows:

1. 6-month – >3.5 to 9 months (106 to 274 days) after randomization
2. 12-month – >9 to 15 months (275 to 456 days) after randomization
3. 18-month – >15 to 21 months (457 to 639 days) after randomization
4. 24-month – >21 to 27 months (640 to 822 days) after randomization
5. 30-month – >27 to 33 months (823 to 1004 days) after randomization
6. 36-month – >33 to 42 months (1005 to 1282 days) after randomization

A visit will be considered missed if it is completed out of window or not completed, but a later visit is completed. There is no analysis window for the 37-month visit. Data from the 37-month visit will be used in analysis if the visit is completed.

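### In the supportive imputation analysis, out-of-window failures are kept but out-of-window passes are redrawn, which contradicts the SAP's own window rule and can only raise failure rates

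*SAP*

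**What the plan says.** Four places in the SAP govern a 36-month exam done outside the analysis window, which section 5.1 sets as "36-month – >33 to 42 months (1005 to 1282 days) after randomization".

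- Section 2.2 item 4: "Data will be considered missing if not completed within the analysis window". It makes no distinction by result, and the primary analysis excludes all such children.
- Table 1, imputation column: all three out-of-window rows read Impute, again without a split by result.
- Section 2.3 item 3: "Data will be imputed for subjects classified as “not failure” at 3 years who meet any of the following criteria". The first criterion is that "the 36-month visit was not completed or was completed out of window".
- Table 1 footnote b, attached to the whole imputation column: data are not imputed "for subjects who have met failure criteria, even if all required testing (initial and retest, with and without correction) has not been completed", and then "If failure criteria were met for any condition, the subjects is considered a failure at 36 months". No window condition is stated.

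Section 2.4 gives the imputation model: logistic regression on prior deterioration, stratified by treatment group, within each cohort.

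**The concern.** Take two children examined on the same out-of-window day, both fully tested. Under item 3 and footnote b, the one who failed is counted as a failure. The one who passed is treated as unknown and receives a draw that can turn into a failure. The draw knows only the child's arm and whether deterioration occurred earlier, which is much less than the exam it replaces. Errors therefore run in one direction only.

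This is the only analysis in the SAP that imputes missing outcomes, because section 2.4 rules out last observation carried forward. Section 2.3 also makes agreement between the primary and additional approaches the condition for treating the primary analysis as definitive. An artefact in the imputation analysis could therefore create or hide an apparent disagreement.

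**Working it through.** **Reading the rules side by side.** Under section 2.2 item 4 and the Table 1 cells, every out-of-window child is imputed. Under item 3 and footnote b, only those who did not fail are. The clash is plainest in the row for an out-of-window visit with a required and completed 37-month visit. Under section 2.1 that visit is required only after a confirmed failure at 36 months. If the child fails again at 37 months, the cell says to impute and footnote b says not to. A programmer cannot follow both.

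**Inputs.** The SAP states no expected failure rate, sample size or out-of-window count, so there is no planned figure to reproduce. The following are assumed:

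- p, the true failure rate: 10–40%
- w, the share of children examined out of window, taken as unrelated to outcome: 2–15%
- q, the imputed failure probability for redrawn children
- no other missing outcomes

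**Formula.** Rate under the one-way rule = (1−w)p + w[p + (1−p)q] = p + w(1−p)q. This exceeds p whenever w and q are above 0 and p is below 1.

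If the imputation model is fitted to everyone not imputed, the retained out-of-window failures enter it, so q = p / [1 − w(1−p)]. The overall rate then equals this same value.

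**Example.** With p = 30% and w = 10%: q = 0.30 / (1 − 0.10 × 0.70) = 0.30 / 0.93 = 0.3226. The rise is 0.10 × 0.70 × 0.3226 = 0.0226, or 2.3 points.

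**Rise in one arm's failure rate (percentage points):**

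| p | w = 2% | w = 5% | w = 10% | w = 15% |
|---|---|---|---|---|
| 10% | 0.2 | 0.5 | 1.0 | 1.6 |
| 20% | 0.3 | 0.8 | 1.7 | 2.7 |
| 30% | 0.4 | 1.1 | 2.3 | 3.5 |
| 40% | 0.5 | 1.2 | 2.6 | 4.0 |

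**Effect on the treatment difference.**

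- Equal p and equal w in both arms: no false difference.
- p = 30% in both arms, w = 5% vs 15%: 33.5% − 31.1% = about 2.4 points of spurious difference. With w = 5% vs 10% it is about 1.2 points.
- A true difference of 15 points (20% vs 35%) with w = 10% in both arms becomes about 15.7 points.

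**Check by simulation.** 2,000,000 children were simulated, with 35% deteriorating and failure rates of 50% if deteriorated and 20% if not. The true rate is 0.35 × 0.50 + 0.65 × 0.20 = 30.5%. Imputation was stratified by deterioration.

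| w | One-way rule | Impute all out-of-window | Keep all observed |
|---|---|---|---|
| 5% | 31.5% | 30.5% | 30.5% |
| 10% | 32.6% | 30.5% | 30.5% |

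Either symmetric rule removes the bias.

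**The case against.** The strongest reply is that the SAP can be read symmetrically. If out-of-window data are missing under section 2.2 item 4, such a child has no exam-based failure status for footnote b to protect. Item 3 also applies its not-failure label to children with no 36-month visit at all, so the label may mean only that failure has not been established. Footnote b's own clause speaks of incomplete testing and does not mention the window. Keeping a confirmed failure when other tests are missing is sensible, because one criterion settles the composite.

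This reading is a real possibility, but it needs a window condition that neither footnote b nor item 3 contains, and footnote b covers the whole column, including the out-of-window rows. At best the SAP supports two analyses with different results.

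Other points on that side stand in full. The analysis is supportive only. The window runs for nine months, so few exams may fall outside it. The size of the effect rests on assumed values. Using every out-of-window result as observed would also depart from the SAP's window rule, whereas imputing them all would not.

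A reader might infer from section 2.4 that the SAP itself expects out-of-window attendance to differ by arm. It does not: that section discusses withdrawal, loss to follow-up and time in the study, not the timing of exams among children who stayed.

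**Conclusion.** The point holds as an internal contradiction with a one-directional consequence, and the wording should be changed. As written, item 3 and footnote b keep out-of-window failures and redraw out-of-window passes, against section 2.2 item 4 and the Table 1 cells.

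The direction is certain for any non-zero imputed failure probability. The size is not known from the SAP. For assumed p of 10–40%, an arm's rate rises by about 0.2–0.5 points at 2% out of window and about 0.5–2.6 points at 5–10%.

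Two stronger conclusions are tempting and not supported. One is that the trial's main result is biased: the primary analysis excludes all out-of-window children, pass or fail, so it is untouched. The other is that the treatment difference is necessarily distorted: that happens materially only if the out-of-window share differs by arm, and nothing in the SAP shows that it does. The 2.4-point example needs an assumed split of 5% vs 15%.

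**What to change.** State one symmetric rule, in the same terms, in section 2.3 item 3, Table 1 and footnote b.

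- **Closest to the existing text:** treat every out-of-window 36-month exam as missing and impute it whatever its result. Limit footnote b's exam-based failures to visits within the window, and drop or qualify the not-failure restriction in item 3 for out-of-window visits. The cost is wording only; section 2.2 item 4 and the Table 1 cells stay as they are. Zero bias here assumes that being out of window is unrelated to outcome, given arm and prior deterioration.
- **Alternative:** use every completed out-of-window result as observed, pass or fail, and impute only where there is no exam or required testing is incomplete. This discards less information, but it changes section 2.2 item 4 and Table 1 for this analysis, and brings in some exams outside 33–42 months.

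Under either option, report the number of out-of-window 36-month exams by arm and by result, so that the reader can see how much the choice could matter. Version 1.0 of the SAP was written after the study was completed. If the analysis has already been run, state which rule was programmed and, if it was the one-way rule, rerun it under the symmetric one.
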